### 11.1.2 Serious Adverse Event (SAE)

An SAE is an adverse event that:

- Results in death. **NOTE:** Death due to disease progression should not be reported as a SAE, unless it is attributable by the site investigator to the study drug(s)
- Is life-threatening (defined as an event in which the subject was at risk of death at the time of the event; it does not refer to an event which hypothetically might have caused death if it were more severe)
- Requires inpatient hospitalization for >24 hours or prolongation of existing hospitalization. **NOTE:** Hospitalization for anticipated or protocol specified procedures such as administration of chemotherapy, central line insertion, metastasis interventional therapy, resection of primary tumor, or elective surgery, will not be considered serious adverse events. Hospitalization for routine treatment or monitoring of the studied indication, not associated with any deterioration in condition (i.e. to perform study related assessments), elective or pre-planned treatment for a pre-existing condition that is unrelated to the indication under study and has not worsened since signing the informed consent, social reasons and respite care in the absence of any deterioration in the subject's general condition or treatment on an emergency outpatient basis that does not result in hospital admission and involves an event not fulfilling any of the definitions of a SAE given above is not a serious adverse event.
- Results in persistent or significant disability/incapacity
- Is a congenital anomaly or birth defect
- Is an important medical event (defined as a medical event(s) that may not be immediately life-threatening or result in death or hospitalization but, based upon appropriate medical and scientific judgment, may jeopardize the subject or may require intervention (e.g., medical, surgical) to prevent one of the other serious outcomes listed in the definition above). Examples of such events include, but are not limited to, intensive treatment in an emergency room or at home for allergic bronchospasm; blood dyscrasias or convulsions not resulting in hospitalization; or the development of drug dependency or drug abuse.

### 11.1.3 Unexpected Adverse Event

For this study, an AE is considered unexpected when it varies in nature, intensity or frequency from information provided in the current IB, package insert, or when it is not included in the informed consent document as a potential risk. Unexpected also refers to AEs that are mentioned in the IB as occurring with a class of drugs or are anticipated from the pharmacological properties of the drug, but are not specifically mentioned as occurring with the particular drug under investigation.

#### 11.1.4 Relatedness

AEs will be categorized according to the likelihood that they are related to the study drug(s). Specifically, they will be categorized using the following terms:

Unrelated	The Adverse Event is not related to the drug(s)
Unlikely	The Adverse Event is doubtfully related to the drug(s)
Possible	The Adverse Event may be related to the drug(s)
Probable	The Adverse Event is likely related to the drug(s)
Definite	The Adverse Event is clearly related to the drug(s)

### 11.2 Procedures for Recording and Reporting Adverse Events

#### 11.2.1 Adverse Events

- AEs will be recorded from time of informed consent until 30 days after discontinuation of study drug(s).
- AEs will be recorded regardless of whether or not they are considered related to the study drug(s).
- All AEs will be recorded in the subject's medical record, AE log in the subject research chart, and on the appropriate study specific eCRF form within OnCore.
- All AEs considered related to study drug(s) will be followed until resolution to  $\leq$  Grade 1 or baseline, deemed clinically insignificant, and/or until a new anti-cancer treatment starts, whichever occurs first.
- All WON sites should follow the AE reporting procedures outlined in the WON Operations Manual in addition to following the non-UW specific procedures outlined above

#### 11.2.2 Reporting of Pregnancy:

- Pregnancy will be reported from time of first study drug until 30 days after discontinuation of either study drug(s).
- Pregnancy will be reported to UW as an SAE **within 1 business day** of discovery of the event.
- Pregnancy follow-up will be reported to UW as follow-up to the initial SAE.

The pregnancy will be followed to determine outcome, including spontaneous or voluntary termination, details of the birth, and the presence or absence of any birth defects, congenital abnormalities, or maternal and/or newborn complications.

Each local site investigator is responsible for informing the IRB and/or other local regulatory bodies of the event as per local requirements.

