- \_\_\_\_ 3.1.11 Females of childbearing potential must have a negative serum pregnancy test within 7 days prior to registration. **NOTE:** Females are considered of child bearing potential unless they are surgically sterile (have undergone a hysterectomy, bilateral tubal ligation, or bilateral oophorectomy) or they are naturally postmenopausal for at least 12 consecutive months.
- \_\_\_\_ 3.1.12 Females of childbearing potential must be willing to abstain from heterosexual activity or must agree to use adequate contraception (hormonal or barrier method) for the duration of study participation and for 90 days after discontinuation of study treatment.
- \_\_\_\_ 3.1.13 Ability of the subject to understand and comply with study procedures for the entire length of the study.
- \_\_\_\_ 3.1.14 Able to swallow ONC201
- \_\_\_\_ 3.1.15 Be willing to discontinue vitamin and mineral supplements for the duration of the study if randomized to receive the methionine restricted diet.

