### **6.3 Protocol therapy discontinuation**

In addition to discontinuation from therapy related to toxicities as outlined in section 6.1, a subject will also be discontinued from protocol therapy and followed up per protocol under the following circumstances:

- Documented disease progression
- Discontinue methionine restricted diet for weight loss grade 2 or higher
- The treating physician thinks a change of therapy would be in the best interest of the subject
- The subject requests to discontinue protocol therapy, whether due to unacceptable toxicity or for other reasons
  - If a subject decides to prematurely discontinue protocol therapy ("refuses treatment"), the subject should be asked if he or she may still be

contacted for further scheduled study assessments. The outcome of that discussion should be documented in the medical records.

- A female subject becomes pregnant
- If protocol therapy is interrupted for >21 days.

Subjects will be removed from protocol therapy, and the site investigator notified, when any of the criteria listed above apply. The reason for discontinuation of protocol therapy will be documented on the eCRF in OnCore.

Subjects who discontinue protocol therapy will be followed every 3 months for 2 years after the end of treatment visit. Survival status and anti-cancer therapy (to include only first cancer directed therapy after study) will be collected from review of medical records or via telephone follow up.

If subjects discontinue study treatment prior to disease progression, scans during follow-up will be completed per standard of care, but RECIST measurements must be completed until disease progression or start of new anti-cancer therapy.

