### 11.2.3 Serious Adverse Events (SAEs)

#### 11.2.3.1 Site Requirements for Reporting SAEs

- SAEs will be reported from time of on-study until 30 days after discontinuation of either study drug(s).
- Any SAEs experienced after this 30-day period will only be reported if the investigator suspects the event is at least possibly related to the study treatment.
- SAEs will be reported to Oncoceutics within 24 hours of discovery of the event. Reporting to the UWCCC will occur per the timelines listed in table 5.
- SAEs include events related and unrelated to the study drug(s).
- All SAEs will be recorded in the subject's medical record and on the appropriate study specific eCRF form within OnCore.
- All SAEs, regardless of relation to study drug, will be followed until resolution to ≤ Grade 1 or baseline and/or deemed clinically insignificant and/or until a new anti-cancer treatment starts, whichever occurs first.
- Recurrent episodes, complications, or progression of the initial SAE will be reported as follow-up to the original episode within 24 hours of the investigator receiving the follow-up information.

Please see section 12.4 for SAE reporting requirements.

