##### 12.4.1.2 Report to the Sponsor:

Serious adverse events (whether or not related to study drugs) will also be reported to Oncoceutics or designee within 24 hours from the time the Investigator first becomes aware of the SAE. After the initial SAE notification to Oncoceutics or designee, follow-up SAE information will be submitted each time that important follow-up information (e.g., diagnosis, outcome, causality assessment, results of specific investigations) becomes available.

Any serious adverse event, or follow up to a serious adverse event, including death due to any cause other than progression of the cancer under study that occurs to any subject from the time of initiation of therapy through 30 days following cessation of treatment, or the initiation of new anti-cancer therapy, whichever is earlier, must be reported to Oncoceutics. This applies whether or not the event is related to ONC201.

If serious medical occurrences, including death, occur outside of the safety follow-up window established by the protocol and are reported to or observed by the Investigator to be related to the administration of the investigational product, it is the Investigator's responsibility to report this occurrence to Oncoceutics or designee within 24 hours from the time site personnel become aware of the occurrence.

In addition to SAEs, the following reportable events must also be submitted to Oncoceutics within 24 hours from the time the Investigator first becomes aware of them:

- Exposure during Pregnancy or Breastfeeding (even if not associated with an adverse event)

- Occupational exposure (even if not associated with an adverse event)  
Reports should be made to Oncoceutics using FDA form 3500A (MedWatch) or the UWCCC SAE form may be used.

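### Section 11.2.2 ends pregnancy reporting to UW, and the outcome follow-up tied to it, 60 days before the protocol's own contraception period ends; the other reporting routes only partly cover the gap

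*Combined protocol and SAP*

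**What the plan says.** Section 11.2.2 states: "Pregnancy will be reported from time of first study drug until 30 days after discontinuation of either study drug(s". A pregnancy in that window goes to UW as an SAE within one business day. Its outcome is then followed through that report: "Pregnancy follow-up will be reported to UW as follow-up to the initial SAE".

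Inclusion criterion 3.1.12 requires women of childbearing potential to abstain or use contraception "for the duration of study participation and for 90 days after discontinuation of study treatment".

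Three other provisions bear on the same period:

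- Section 12.4.1.2, on reports to the drug supplier, says "the following reportable events must also be submitted to Oncoceutics within 24 hours from the time the Investigator first becomes aware of them" and lists "Exposure during Pregnancy or Breastfeeding (even if not associated with an adverse event". It gives no end date for this item.
- Section 11.1.2 counts as an SAE any adverse event that "Is a congenital anomaly or birth defect". Under 11.2.3.1, SAEs more than 30 days after discontinuation "will only be reported if the investigator suspects the event is at least possibly related to the study treatment".
- Section 6.3 sets the later contacts: "Subjects who discontinue protocol therapy will be followed every 3 months for 2 years after the end of treatment visit". The data named there are survival status, the first later anti-cancer therapy, and RECIST measurements where treatment stopped before progression. Records or a telephone call may supply the follow-up data.

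**The concern.** The protocol asks women to avoid conception for 90 days after treatment, but it requires sites to tell UW about a pregnancy for only the first 30. Someone who follows 11.2.2 exactly has no duty under it to report a pregnancy arising on day 45. Since outcome follow-up depends on the initial report, nothing in that section would then require the birth, any termination, or any maternal or newborn complication to be recorded.

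The trial enrols only women, from age 18. A final statement that no pregnancies were reported to UW would rest on one third of the post-treatment period in which the protocol itself asked for contraception.

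The sentence has two further ambiguities. It does not say whether the date of conception or of discovery must fall inside the window. It also counts from stopping either of the study drugs, in a trial with one drug and a diet.

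**Working it through.** No sample size, power or event count is involved. The check compares the stated windows and then looks for any other provision that covers the difference.

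**Windows after discontinuation**

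| Provision | End of window | What it requires |
|---|---|---|
| 3.1.12 | day 90 | contraception or abstinence |
| 11.2.2 | day 30 | report to UW; outcome follow-up depends on this |
| 11.2.3.1 | day 30, then only if judged possibly related | SAE report |
| 12.4.1.2, pregnancy exposure | none stated | supplier report within 24 hours of awareness |

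Difference between 3.1.12 and 11.2.2: 90 − 30 = 60 days (days 31 to 90). As a share of the post-treatment contraception period: 60/90 = 67%. This is a share of calendar days, not of expected pregnancies or of drug exposure.

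**Do the other routes close the gap?**

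1. *Supplier report (12.4.1.2).* It has no cut-off, but it applies only once the investigator is aware. It does not say whether conception after the last dose is exposure, and it sets no pregnancy-outcome follow-up. It also sits under the heading for events at UWCCC. For WON sites, 12.4.3.2 and 12.4.4.2 make the UW Principal Investigator responsible for telling the supplier of SAEs, so UW must hear first. The site's pregnancy duty to UW ends at day 30.
2. *Congenital anomaly as an SAE (11.1.2 with 11.2.3.1).* After day 30 this needs someone to learn of the birth and to judge it possibly related.
3. *Scheduled contacts (section 7 and 6.3).* The serum pregnancy test is listed only at screening and cycle 1 day 1. The end-of-treatment visit falls at day 35 ± 5 after the last dose, that is days 30 to 40, with no pregnancy test. Long-term follow-up lists no pregnancy item.

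**When the first 3-monthly follow-up falls.** Taking 3 months as about 91 days: 35 + 91 = day 126 after the last dose. With the stated tolerances (± 5 and ± 7 days) the range is 30 + 91 − 7 = day 114 to 40 + 91 + 7 = day 138. Every value is past day 90.

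**Which stop starts the clock.** The word either presupposes two study drugs. Table 2 lists the methionine-free food as an agent, and section 6.1 lets a subject stop the diet and stay on ONC201. If the diet counts, the 30 days could begin, and expire, while ONC201 continues. Section 11.2.3.1 uses the same expression for SAEs.

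**Number of women.** The share of childbearing potential is not given. At an assumed 20% to 40% of 34 subjects: 34 × 0.20 = 6.8 and 34 × 0.40 = 13.6, so about 7 to 14 women. This is the group to which the rule applies, not a forecast of pregnancies.

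**The case against.** The strongest reply is that the protocol does not leave days 31 to 90 empty. The supplier duty in 12.4.1.2 has no end date, so on its face it reaches beyond day 90. The same section requires related serious occurrences outside the safety window to be reported. Section 11.2.2 treats pregnancy as an SAE, and possibly related SAEs stay reportable after day 30, with timelines in 12.4. A reader might infer that pregnancies in this period go wholly unreported and unfollowed. The documents do not support that. What remains is that these routes depend on awareness or judged relatedness, and that none sets outcome follow-up of the pregnancy itself.

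A second reply is that 90 days is a contraception rule. The protocol never calls it a risk period. Section 1.5.3 gives a mean half-life of 11.3 h (SD 5.2). Day 30 is 720/11.3 ≈ 64 half-lives after the last dose, and 720/21.7 ≈ 33 at the mean plus two SDs (11.3 + 2 × 5.2 = 21.7 h). This does not show that later risk is absent, but it means that conceptions on days 31 to 90 cannot be called exposures on the documents alone. The 30 days also match the AE and SAE windows in 11.2.1 and 11.2.3.1. That may explain where the figure came from, but it does not explain why it differs from 3.1.12.

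A third reply is that follow-up may be by record review, so an added question cannot assume that a patient contact already takes place. That stands and bears on the cost.

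**Conclusion.** The mismatch is real and unexplained. The UW reporting and outcome follow-up window in 11.2.2 is 60 days shorter than the contraception period in 3.1.12, and the remaining routes are partial. The ambiguity over conception or discovery date, and over which stop starts the clock, could shorten the window further on some readings.

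This is an inconsistency between safety-reporting sections. It does not show that the protocol lacks any route after day 30, or that two thirds of fetal risk goes unmonitored. Nor does it show which duration is right. Few events are expected, and no efficacy endpoint, stopping rule or analysis is affected. The conclusion rests only on the stated windows. The 7 to 14 women are an assumption and carry no weight in it.

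**What to change.** Reconcile 3.1.12, 11.2.2, 11.2.3.1 and 12.4.1.2:

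- In 11.2.2, run the reporting and outcome follow-up window to the end of the protocol's own contraception period, or state why it is shorter.
- Define the window by date of conception, whenever the pregnancy is discovered.
- Count it from the last protocol treatment, replacing the reference to either study drug.
- Leave the supplier duty in 12.4.1.2 open-ended, because a 90-day limit there could narrow it. Cross-refer it to 11.2.2 and say whether conception after the last dose counts as exposure.
- For women of childbearing potential, add a pregnancy check to the first 3-monthly follow-up (about day 126 after the last dose), by telephone or record review as 6.3 already allows.

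The cost is a wording amendment, one added item at a scheduled follow-up and a few possible extra reports. Where that follow-up would have been a chart review, it may also mean a short call.

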### 11.2.3 Serious Adverse Events (SAEs)

#### 11.2.3.1 Site Requirements for Reporting SAEs

- SAEs will be reported from time of on-study until 30 days after discontinuation of either study drug(s).
- Any SAEs experienced after this 30-day period will only be reported if the investigator suspects the event is at least possibly related to the study treatment.
- SAEs will be reported to Oncoceutics within 24 hours of discovery of the event. Reporting to the UWCCC will occur per the timelines listed in table 5.
- SAEs include events related and unrelated to the study drug(s).
- All SAEs will be recorded in the subject's medical record and on the appropriate study specific eCRF form within OnCore.
- All SAEs, regardless of relation to study drug, will be followed until resolution to ≤ Grade 1 or baseline and/or deemed clinically insignificant and/or until a new anti-cancer treatment starts, whichever occurs first.
- Recurrent episodes, complications, or progression of the initial SAE will be reported as follow-up to the original episode within 24 hours of the investigator receiving the follow-up information.

Please see section 12.4 for SAE reporting requirements.

## 12. DATA AND SAFETY MONITORING PLAN

### 12.1 Oversight and Monitoring Plan

The UWCCC Data and Safety Monitoring Committee (DSMC) is responsible for the regular review and monitoring of all ongoing clinical research in the UWCCC. A summary of DSMC activities are as follows:

- Reviews all clinical trials conducted at the UWCCC for subject safety, protocol compliance, and data integrity.
- Reviews all Serious Adverse Events (SAE) requiring expedited reporting, as defined in the protocol, for all clinical trials conducted at the UWCCC, and studies conducted at external sites for which the UWCCC acts as an oversight body.
- Reviews reports generated through the UWCCC DSMS elements (Internal Audits, Quality Assurance Reviews, Response Reviews, Compliance Reviews, and Protocol Summary Reports).
- Notifies the protocol Principal Investigator of DSMC decisions and, if applicable, any requirements for corrective action related to data or safety issues.
- Works in conjunction with the UW Health Sciences IRB in the review of relevant safety information as well as protocol deviations, non-compliance, and unanticipated problems reported by the UWCCC research staff.

- Ensures that notification of SAEs requiring expedited reporting is provided to external sites participating in multi-institutional clinical trials coordinated by the UWCCC.

## **12.2 Monitoring and Reporting Guidelines**

UWCCC quality assurance and monitoring activities are determined by study sponsorship and risk level of the protocol as determined by the PRMC. All protocols (including Intervention Trials, Non-Intervention Trials, Behavioral and Nutritional Studies, and trials conducted under a Training Grant) are evaluated by the PRMC at the time of committee review. UWCC monitoring requirements for this trial are as follows:

### **12.2.1 Intermediate Monitoring**

Protocols subject to intermediate monitoring generally include UW Institutional Phase I/II and Phase II Trials. These protocols undergo review of subject safety at regularly scheduled DOT meetings where the results of each subject's treatment are discussed and the discussion is documented in the DOT meeting minutes. These discussions may include the number of subjects enrolled, significant toxicities, dose adjustments, and responses observed. Protocol Summary Reports are submitted on a semi-annual basis by the study team for review by the DSMC.

## **12.3 Review and Oversight Requirements**

### **12.3.1 Serious Adverse Event – Reported within 24 Hours**

Serious Adverse Events requiring reporting within 24 hours (as described in the protocol) must also be reported to the Data and Safety Monitoring Committee (DSMC) Chair via an email to [[contact]](mailto:[contact]) within one business day. The OnCore SAE Details Report must be submitted along with other report materials as appropriate (NCI AdEERS form or FDA Medwatch Form #3500 and/or any other documentation available at that time of initial reporting). The DSMC Chair will review the information and determine if immediate action is required. Within 5 calendar days, all available subsequent SAE documentation must be submitted electronically along with a 24-hour follow-up SAE Details Report and a completed UWCCC SAE Routing Form to [[contact]](mailto:[contact]). All information is entered and tracked in the UWCCC database.

The Principal Investigator notifies all investigators involved with the study at the UWCCC, the IRB, the sponsor, and the funding agency and provides documentation of these notifications to the DSMC. If the SAE occurs on a clinical trial in which the UW PI serves as the sponsor-investigator, the PI reviews the event to determine whether the SAE requires reporting to the FDA and other participating investigators. For a multiple-institutional clinical trial the PI is responsible for ensuring SAEs are reported to the FDA as well as to all participating investigators.

